and slowly titrated up to maintenance dose. Gabapentin has been used successfully to treat neuropathic pain and perioperative pain ¹³. It has been shown to reduce stroke size, decrease the cortical spreading depression (CSD), which in turn can cause vasospasm and delayed ischemic neurologic deficit (DIND) ¹⁴. Mayo Clinic Jacksonville has been using gabapentin in order to reduce the narcotic requirement and complication. In our retrospective chart review in neurocritical care ICU (NICU) from January 2011 till February 2013, study (53 patients) there was 6% nausea (intolerable in 1.9%) but no major adverse effects of gabapentin maintenance dose (1800-2700mg /day). We also found a decrease in mean use of opioids with the use of gabapentin within the first 4 days post SAH compared to after 5 days (P = 0.01) . There was no fall, dizziness and abnormal liver function associated with the use of gabapentin. Aseptic meningitis was detected with the analysis of cerebrospinal fluid (CSF) during the second half of the ICU stay. The cost of 300mg of gabapentin was average of 30 times less than intravenous fentanyl 100 mcg. We did not find any other study looking at the use of gabapentin in aSAH patients.

The plan is to conduct a randomized control trial with a total of 20 aSAH patients. 10 aSAH patients admitted in NICU will be assigned to receive gabapentin, and 10 will receive placebo. Both of the groups will receive standard of care for pain control for 7 days.

Hypothesis: “Gabapentin will reduce the pain score and narcotics requirement_among hospitalized aSAH patients compared to placebo alone.”

The primary specific aims and hypothesis of this study are:

1. To compare the narcotic requirements among SAH patients experiencing headache treated with gabapentin or placebo for 7 days.
2. To compare efficacy of gabapentin in reducing the headache numeric pain score (NPS) compared to the non-GBP arm among hospitalized aSAH patients. Both groups are treated by an existing standard of care algorithm with narcotics and NSAIDs.

The secondary aims of this study are:

1. To evaluate the initial dose, escalation and side effects of gabapentin (nausea, vomiting, fall, lightheadedness, dizziness, vertigo, confusion).
2. To evaluate the incidence of delirium, vasospasm, delayed ischemic neurologic deficit (DIND) and seizure among hospitalized aSAH patients.
3. To evaluate the incidence of aseptic meningitis with cerebrospinal fluid (white blood cell and red blood cell ratio).

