Narcotic Requirement: We will use intravenous fentanyl as a pain medication. The dose range of fentanyl will be from 25 micrograms to 50 micrograms, which could be repeated hourly. Total daily requirement of fentanyl for head and neck pain will be calculated every day. The side effects of the fentanyl will be prospectively charted. We plan to use subsequent line of pain management as describe in the text above if not controlled by fentanyl or have side effects with it.

Laboratory variables: Whenever cerebrospinal fluid (CSF) is collected by standard of care via an external ventricular drain or lumbar specimen. We will review this data for white blood cell (WBC), red blood cell (RBC) counts, as well as the CSF WBC/RBC ratio and culture and sensitivity. We will also review values of kidney function (creatinine and BUN), in the medical record performed as standard of care by the treating team.

Radiological variables: We will review patient CT or CT angiography done by standard of care by the treating team. We plan to get SAH severity using the Fisher grade, aneurysm location, follow up CT angiography and/ or transcranial Doppler for detection of vasospasm.

Aseptic Meningitis Screening: In order to screen that meningitic pain after aSAH was not due to from frank bacterial (septic) meningitis, CSF data will be reviewed from existing external ventricular drain (EVD) or CSF samples especially when there is fever and headaches documented in the electronic health record. The CSF culture result will also be analyzed to rule out any bacterial meningitis or ventriculitis. When CSF WBC is elevated and culture is negative for microorganisms, with persisting headache, these groups will be defined as 'aseptic' or inflammatory meningitis. Any patient who develops bacterial meningitis will be excluded from final headache analysis since the pathology will be different. The incidence of bacterial meningitis in SAH patients with EVD is < 1.0% and unlikely given the small sample size of this study. Also GBP medication is not expected to in any way increase the risk of bacterial meningitis based on our retrospective study and existing FDA safety data on GBP.

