Gabapentin escalation dosing will be modeled after our retrospective safety study. We will start with 100 mg orally three times a day then every 24 hours increase to 300 mg tid as tolerated, then 600 mg tid and to a maximum of 900 mg tid. We plan to use 100mg tid then 200 mg tid and 400mg tid if creatinine clearance of 30 -59. We will exclude any patients who have CrCl <30. We will define maintenance dose of GBP as a dose in which after being on it for 24 hours there is 50% reduction of daily average NPS. We will continue maintenance dose throughout hospital stay. aSAH patients will be in observation in NICU for median of 15 days. The placebo will be escalated in the same manner as GBP. A Mayo pharmacist would dispense the study drug (ie., GBP or placebo). Every patients discharged with aSAH will be followed by Mayo neurologist as a SOC and they will plan to reduce or stop GBP.

C.6. Data Analysis

Unless otherwise specified, analyses will be performed using an intention-to-treat approach whereby subjects are analyzed according to randomized treatment arm. The primary endpoint for this trial will be the 7 days of treatment with or without GBP and best medical therapy. For this endpoint the treatment groups will be compared using a two-tailed test with a p -value ≤ 0.05 .

Categorical variables will be summarized as percentages, and continuous factors will be described using means or medians to best describe the distributions. Adverse events will be described as rates, and 95% confidence intervals estimated for those rates. The calculated total daily NPS score; opioid requirement and GBP dose will be analyzed. CSF WBC/RBC ratio will be calculated from the available sample and trended on days of SAH. All the plotted data will be projected with a 95% confidence interval.

We will compare the NPS, patient satisfaction score and the fentanyl requirement among the GBP and placebo group. We will use 2 sample t test or Wilcoxon rank sum test. The data will be analyzed to see if there is difference in incidence of aseptic meningitis, vasospasm and DIND between the GBP and placebo group. If there is difference more than 5 %, we will use regression modeling to analyze the data.

C.7. Sample Size Considerations

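### Aseptic meningitis, a secondary outcome compared between arms, requires persisting headache, so pain relief alone can lower its recorded incidence

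*Combined protocol and SAP*

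**What the plan says.** Four places in the combined protocol and SAP bear on this.

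- **Section 2, secondary aim 3:** "To evaluate the incidence of aseptic meningitis with cerebrospinal fluid (white blood cell and red blood cell ratio". The aim is worded in CSF terms and does not mention headache.
- **Section C.4, Aseptic Meningitis Screening:** a patient is classed as having aseptic or inflammatory meningitis "When CSF WBC is elevated and culture is negative for microorganisms, with persisting headache". This is the only operational definition. It joins three conditions, and the third has no pain-score threshold, duration or time window.
- **Section C.6:** the data are to be examined for a "difference in incidence of aseptic meningitis, vasospasm and DIND between the GBP and placebo group".
- **Section 2, second primary aim:** "To compare efficacy of gabapentin in reducing the headache numeric pain score (NPS) compared to the non-GBP arm among hospitalized aSAH patients".

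Section A.2 describes aseptic meningitis as sterile meningeal inflammation that may be accompanied by fever and headache. There headache is a possible accompaniment; in C.4 it is a requirement. C.6 also plans to trend the CSF WBC/RBC ratio by day, but states no between-arm test of the ratio and no incidence based on CSF alone.

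**The concern.** One component of this secondary outcome is the symptom that the treatment targets. The paragraph in C.4 was written to separate sterile from bacterial meningitis, and a headache condition may suit that screening purpose. It does not suit a randomised comparison of how often meningeal inflammation occurs, because treatment can change case status without changing the CSF.

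The risk lies in interpretation. Section A.3 raises a possible anti-inflammatory action of gabapentin. Fewer cases on gabapentin would invite that reading, although they might only repeat the pain-score result under another name. The rule could also hide a difference in the other direction. Ketorolac and dexamethasone are the third and fourth tiers of the standard pain regimen in C.2. If better pain control meant less use of them, CSF inflammation could be higher on gabapentin while the headache condition removed some of those cases from the count.

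**Working it through.** The documents give no rate, effect size or power for aseptic meningitis, so there is no figure of the plan's own to reproduce. The check is algebraic, followed by an illustration.

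**Identity.** For each arm let

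- q = probability of raised CSF WBC with negative culture;
- h = probability of persisting headache among those CSF-positive patients.

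Under C.4 the recorded incidence is q × h. If q is the same in both arms,

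risk ratio = (q × h_gabapentin) / (q × h_placebo) = h_gabapentin / h_placebo.

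CSF positivity cancels and only headache remains. Because h is conditional on a positive CSF, this does not require headache and CSF findings to be independent. A CSF-only definition gives q / q = 1.00.

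**Illustration.** All rates are assumptions.

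| CSF-positive, both arms | Headache persists, placebo vs gabapentin | Recorded incidence | Difference | Risk ratio |
|---|---|---|---|---|
| 40% | 90% vs 90% | 36% vs 36% | 0 points | 1.00 |
| 40% | 90% vs 60% | 36% vs 24% | 12 points | 0.67 |
| 50% | 80% vs 60% | 40% vs 30% | 10 points | 0.75 |
| 50% | 80% vs 40% | 40% vs 20% | 20 points | 0.50 |

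Second row: 0.40 × 0.90 = 0.36; 0.40 × 0.60 = 0.24; 0.24 / 0.36 = 0.67.

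**Scale.** Section C.7 plans 10 patients per arm. If all have CSF sampled, 12 points is 0.12 × 10 = 1.2 patients. The standard error of the difference is √(0.36 × 0.64/10 + 0.24 × 0.76/10) = √0.0413 = 0.20, or 20 points. The artefact is therefore a tilt in direction and would seldom be a significant result. By exact binomial calculation with 10 per arm, gabapentin shows fewer cases in 64% of trials at 36% vs 24%, against 41% when both arms have a CSF-only rate of 40%. At 40% vs 20% the figure is 78%, against 41% with a CSF-only rate of 50% in both arms.

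**The case against.** The strongest reply is that the effect may be small or absent.

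- **Undefined term.** C.2 treats a 50% fall in pain score as meeting the study goal. A patient who falls from 8 to 4 meets it and still has headache. If any non-zero score counts as persisting headache, few or no classifications change.
- **Rescue.** Both arms receive the tiered regimen in C.2, which narrows any headache difference.
- **Timing.** Section 2 places aseptic meningitis in the second half of the ICU stay, and C.1.b reports later pain peaks on days 11 and 16 after the bleed. Dosing starts the morning after randomisation, which falls within 72 hours of admission, and blinding ends after 7 days. That is at most about 3 + 1 + 7 = 11 days from admission, after which placebo patients may receive gabapentin.
- **Retrospective data.** The patients in C.1.b were all on gabapentin, yet those later peaks coincided with a high CSF ratio. Headache may persist on gabapentin just when the CSF is abnormal.

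All of this stands as a limit on size. It is why the point is that pain relief can lower the recorded incidence, not that it will. None of it removes headache from the definition.

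Three stronger readings are tempting, and the documents do not support them.

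- A reader might infer that headache decides whose CSF is reviewed, since C.4 mentions review "especially when there is fever and headaches documented in the electronic health record". The Laboratory variables paragraph of the same section says that CSF data are reviewed whenever CSF is collected as standard of care, so the phrase is one of emphasis and not a selection rule.
- A reader might vary CSF positivity from 30% to 50% and quote an artefact of 9 to 15 points (0.30 × 0.30 to 0.50 × 0.30). That holds the headache rates at 90% vs 60%, which are the assumptions that matter most; with equal headache rates the answer is 0.
- A reader might measure the artefact against the rule in C.6, "If there is difference more than 5 %, we will use regression modeling to analyze the data". With 10 per arm one patient is 10 points, and the rule is met in about 82% of trials with identical 50% rates, so crossing it says nothing about this problem.

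**Conclusion.** The definition is circular for a between-arm comparison and does not match the wording of aim 3. Where CSF positivity is equal in the two arms, the risk ratio for recorded aseptic meningitis is the risk ratio for persisting headache among CSF-positive patients. That follows from the definition and needs no assumed rate.

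The size cannot be derived from the documents. It runs from nothing upward, depending on how persisting headache is read and how far gabapentin changes it; 36% against 24% is one assumed case, worth about one patient in ten.

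C.2 and section 2 state the hypothesis and goal in terms of pain score and narcotic use, and section B calls the neuroprotection data exploratory and underpowered. The consequence is confined to the interpretation of secondary aim 3; the primary aims are untouched. It should be corrected because the correction is cheap, not because it threatens the trial.

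**What to change.** For the comparison in C.6, define aseptic meningitis on CSF alone:

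- one criterion chosen in advance, either a WBC threshold or a WBC/RBC threshold, not a choice between them;
- negative culture;
- a fixed window, ideally the blinded 7 days;
- applied to all CSF collected under standard of care, whatever the symptoms.

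Report the number of patients sampled in each arm. Report the version that also requires persisting headache descriptively only, and state what counts as persisting.

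The cost is a change of wording in C.4 and C.6 and the choice of a threshold; no new sampling is needed. There are two small downsides. CSF-positive patients without symptoms will count as cases. A threshold set too low could label most sampled patients, since A.2 describes a white-cell response to blood as part of the usual course. A 7-day window will also miss some late cases, but a longer one would mix in open-label gabapentin in the placebo arm.

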In patients with a normal creatinine clearance (CrCl) \geq 60 ml/min the study medication will be started at 100 mg three times a day and if headache is not controlled by study day #2, it will be increased to 300mg three times a day. For headaches that are still not controlled by day 3, study medication will be increased to 600 mg three times a day and by day 4, 900 mg three times a day. For the purposes of this study, a maximal dose of 900 mg tid in patients with normal kidney function (2700mg/day) even though the package insert describes 3600mg/day as maximal. For patients with a CrCl of 30 -59 ml/min, we will use an initial dose of 100mg tid day #1, then 200 mg tid by day #2 if pain uncontrolled, and 400mg tid if by day #3 if pain still uncontrolled. This dose of 1200mg/day would be the maximal dose used for these patients if CrCl remains within the 30-59ml/min range. We will exclude any patients who have CrCl $<$ 30 ml/min. When patients have achieved a 50% reduction of NPS, this will be defined as the maintenance dose and no escalation of GBP will be done after that, unless there is headache worsening. Placebo pills will be given three times a day and SOC pain management performed as indicated above in the control arm. The pharmacist or nurse will dispense the study drug. The bedside nurse will record the numeric pain score (NPS) 0-10, 0 being no pain and 10 being worst pain every 4 hours per hospital policy but done on a bedside data collection form as well for the purposes of the study. Total score over 24 hours will be averaged as daily score. Decision to increase the GBP will be based on 24 hour score communicated by the treating team as part of morning rounds by calling the central pharmacy.

After the 7 day study period, patients will be unblinded to either arm and those on gabapentin may remain on the medication if pain is controlled. However patients in the placebo arm-- if still in pain-- after 7 days may be treated with gabapentin up-titration similar to the treatment arm but used as standard of care. Patient's pain scores will also be recorded after the 7 day randomized period for observational purposes to examine for crossover effect (the proportion of those within the placebo arm who are placed on gabapentin). Analysis of these groups will be based on intention to treat principle.

C.3. Participants

Inclusion Criteria:

1. 18 years of age or older

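### Dropping patients who develop bacterial meningitis from the headache analysis is a pre-declared but avoidable departure from intention-to-treat, with no time window and a probably small effect.

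*Combined protocol and SAP*

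**What the plan says.** All references are to the combined protocol and SAP.

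- **The exclusion.** C.4, under Aseptic Meningitis Screening: "Any patient who develops bacterial meningitis will be excluded from final headache analysis", on the ground that the disease process differs. The same paragraph puts the incidence of bacterial meningitis in SAH patients with an EVD below 1.0%, calls a case unlikely in a study this small, and does not expect gabapentin to raise the risk.
- **How cases are looked for.** That paragraph has existing CSF data reviewed "especially when there is fever and headaches documented in the electronic health record", with culture used to rule out bacterial infection. The Laboratory variables paragraph of C.4 is broader. It provides for review of cell counts and culture as follows: "Whenever cerebrospinal fluid (CSF) is collected by standard of care via an external ventricular drain or lumbar specimen".
- **The analysis principle.** C.6: "Unless otherwise specified, analyses will be performed using an intention-to-treat approach whereby subjects are analyzed according to randomized treatment arm". C.2, after describing follow-up beyond day 7, adds: "Analysis of these groups will be based on intention to treat principle".
- **The outcome affected.** Section 2 lists headache numeric pain score (NPS) as a primary aim, beside narcotic requirement. The exclusion names only the headache analysis.
- **Timing.** Randomisation is within 72 hours of admission and unblinding follows the 7-day period (C.2). The primary endpoint covers 7 days (C.6). Median observation in the unit is 15 days (C.5).

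**The concern.** The rule takes randomised patients out of a primary comparison because of something that happens after randomisation. That the disease process differs is a reason to want a second look without these patients. It is not a reason to remove them from the comparison that randomisation protects.

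Three features make the rule looser than it need be:

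1. It has no cut at diagnosis. A patient infected on day 6 would lose five days of valid scores as well as the affected ones.
2. It has no time window. With a 7-day endpoint and a median stay of 15 days, a case can be found once the arm is known, and the rule would then delete a complete 7-day record.
3. No analysis that keeps these patients is planned, and nobody blind to arm is assigned to decide who counts as a case.

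There is also a possible route to bias. CSF is sampled only in routine care, and headache may prompt sampling. If gabapentin relieves headache, placebo patients might be sampled more often, and a true infection might be found in one arm and missed in the other.

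**Working it through.** The documents give no figure for the effect of this exclusion, so there is none to reproduce. The sample size in C.7 is unaffected by the fix: it stays at 10 per arm.

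**Inputs.** 20 patients, 10 per arm (C.7). Incidence below 1.0%, stated only for patients with an EVD (C.4). SD of pain score 5.84, scale not stated (C.7). The number of patients with an EVD is not given, so a range is shown.

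**Chance that the rule is triggered.** P(at least one case) = 1 − (1 − p)^m, where m is the number of patients at risk.

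| Assumption | Calculation | Result |
|---|---|---|
| 1.0% ceiling, all 20 at risk | 1 − 0.99^20 | 18.2% |
| 1.0% ceiling, 10 with an EVD, others negligible | 1 − 0.99^10 | 9.6% |
| 1.0% ceiling, 5 with an EVD, others negligible | 1 − 0.99^5 | 4.9% |
| 0.5% assumed, all 20 at risk | 1 − 0.995^20 | 9.5% |

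In the first row the expected number removed is 20 × 0.01 = 0.2, and the chance of two or more is 1.7%.

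**Effect of one removal on the estimate.** One patient is 1/10 = 10% of an arm. If that patient's score lies D points from the mean of the other nine, removal moves the arm mean by D/10; for D = 5 that is 0.5 points. For the worst case, assume normal scores and remove the highest of ten. The expected maximum is 1.54 SD above the mean, so the other nine average 1.54/9 = 0.17 SD lower. The standard error of the difference between arms is √(2/10) = 0.45 SD, so this worst shift is 0.17/0.45, or about 0.4 of a standard error. Weighted by the 9.6% chance of a case in one arm of ten at the 1.0% ceiling, it averages 0.096 × 0.17 = 0.016 SD.

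**Effect on power.** C.7 gives no absolute difference. Taking 7.5 points as an assumption (25% of a daily total of 30) with SD 5.84, two-sided 5% and the normal approximation, going from 10 v 10 to 10 v 9 lowers power from 81.9% to 79.8%. With the t test it falls from 77.5% to 75.0%. Lost power is therefore not the main issue.

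**Detection, with the two C.4 paragraphs side by side.** The screening paragraph stresses fever and headache. The Laboratory variables paragraph covers CSF whenever routine care collects it. Together they mean that collected CSF is reviewed whatever the headache. Headache could influence detection only through the clinical decision to take a sample, which the documents do not describe.

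**The case against.** The strongest defence is that C.6 allows stated exceptions and C.4 states one in advance, with a reason and an expected frequency. This stands. A reader might infer that C.4 contradicts C.6 or breaks intention-to-treat unannounced; the documents do not support that. It is a declared departure. Declaring it, however, does not restore the randomised comparison for the headache outcome.

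A reader might also infer that removal depends on the outcome and so biases the trial. The documents do not support that either:

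- High pain alone removes nobody. The patient must actually develop bacterial meningitis. Persisting headache with raised white cells and a negative culture is classed as aseptic and kept.
- Every patient enters with headache and NPS of at least 5 (C.3), so the presence of headache separates patients poorly.
- Gabapentin is not expected to raise the infection risk, and staff in contact with patients are blinded during treatment.

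If neither the event nor its detection differs by arm, the exclusion does not systematically favour either arm. A difference in detection through the decision to sample remains possible but is not demonstrated.

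Finally, the event is rare and the rule will most likely never be used. That also stands, and it sets the severity. It does not answer the loss of pre-infection scores or the missing time window, and it means that keeping these patients costs little.

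**Conclusion.** The point holds as a minor one. C.4 excludes randomised patients from a primary outcome for a post-randomisation event, with no cut at diagnosis, no time window and no analysis that retains them. The exclusion is pre-declared, and bias between arms is possible but not shown.

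The size rests on two assumptions that should travel with the numbers. The chance of any removal, at most about 18%, extends to all 20 patients a ceiling stated only for those with an EVD; it is about 10% if half have one and the others have negligible risk. The shift of 0.17 SD assumes normal scores and that the removed patient is the highest of ten. It is a worst case given a removal, not an expected bias. The rule names only the headache analysis, so nothing here shows that the narcotic comparison is affected, although the two primary aims could end up analysed on different sets of patients.

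**What to change.** Replace the exclusion sentence in C.4 with a statement that every randomised patient stays in the primary NPS analysis, by randomised arm, over the 7 days. Add a sensitivity analysis that omits bacterial-meningitis cases or cuts their scores at diagnosis. Say there what counts as a case for this purpose, and have that judged blind to arm.

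The cost is a small edit to C.4 and one extra analysis. Keeping these patients may slightly dilute the comparison with infection-related pain; the sensitivity analysis shows by how much. The sample size and patient care do not change.

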This study will be a randomized, placebo-controlled clinical trial enrolling 20 subjects at MCF to either GBP + standard of care (SOC) vs placebo + SOC arm. While enrolling the patients we will stratify patients via numerical pain score (NPS) to either <5 or ≥ 5 . Patients with an NPS ≥ 5 will be randomly assigned to either GBP or placebo group within 72 hours of SAH admission and after informed consent. The SOC pain regimen is comprised of intravenous (IV) fentanyl 25mcg to 50mcg q1hr PRN for head and neck pain as the first-line agent. If SAH pain remains >5 on NPS after the next nursing pain assessment, the next tier of pain agents will be utilized consisting of the following tier:

2nd line- enteral /PO oxycodone 5mg PRN q4hrs pain, and if still in pain after next assessment, then 10mg q4hrs PRN,

3rd line (if 2nd line failed to reduce NPS < 5)- IV 15mg ketorolac q6hrs PRN x 24hrs, unless serum creatinine > 1.3 , or GFR < 30 , or concern for gastrointestinal bleed risk, or history of bleeding peptic ulcer.

4th line (if 3rd line failed to reduce NPS < 5)- dexamethasone 2mg IV BID x 24hrs.

The patient will be enrolled within 72 hours of admission and meeting inclusion criteria by investigator and coinvestigators. Documentation of numeric pain score will be done by standard of care per nursing and hospital policies in the medical record. After consent and enrollment, a data collection sheet will be recorded by nursing to summate the NPS scores every 24 hours along with the SOC pain management plan. The SOC pain management plan will be implemented by the NeuroICU team of residents, attending, and nurse practitioners/PA's who are available on a 24/7 basis. A decrease in pain score equal or more than 50% will be defined as meeting the goal of the study, and as headache pain being under control. Patients will begin study medication (gabapentin or placebo) at approximately 9:00 AM on the morning following randomization into the trial to allow for documentation of the baseline average NPS. The

baseline NPS will be used to determine if the patient has had a 50% or more decrease in pain score.

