2. Have aneurysmal SAH diagnosed by CT scan of the brain and/or angiogram evidence of intracranial aneurysm (CTA or digital subtraction angiogram or MRA)
3. Have symptomatic headache
4. Able to swallow and verbalize pain score
5. No known allergy to GBP or fentanyl
6. Numeric pain score \geq 5
7. Ability to provide written personal consent

Exclusion Criteria:

1. GBP use prior to SAH admission
2. Renal failure with creatinine clearance less than 30 ml/min
3. Unable to receive standard of care pain medications
4. Pregnant patients
5. History of severe depression defined by DSM IV

C.4. Study Procedures & Schedule

All study medication will be labeled and dispensed according to subject number ensuring that treatment assignment remains concealed to the subject, investigator, and all study personnel who have subject contact. Data collection will be done in case report form at the bedside and

later will be enter in spread sheet. We will issue unique ID for each study patients. 20 preprinted study ID labels will be used to randomly select study patients.

Subject selection: All aneurysmal SAH admitted will be screened by the Mayo Cerebrovascular laboratory for eligibility and the NeuroICU attending and/or fellow will be contacted about potential enrollment in the study. Subjects who are able to provide written consent will be approached for enrollment. Based on prior volumes, we expect to have 20 subjects enrolled within 6-9 months.

Pain assessment: We will use numeric pain scale (NPS) that is been validated in many studies and is easy to use. Nurse and medical staff are familiar with this scale in our institute as it has been commonly used as standard of care. We plan to perform this pain scale every 4 hours in the study patients. The scale range from 0-10, 0 being the no pain and 10 being the worst pain ever. We will calculate daily total score for each patient. Only headache and neck pain will be included in the study to calculate the pain score. We will not include the score for other pain like back and abdominal pain.

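### C.6 names a 7-day treatment period as the primary endpoint, leaving the 7-day summary measure and the success rule for pain and narcotics undefined

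*Combined protocol and SAP*

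**What the plan says.** All references are to the combined protocol and SAP.

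- **C.6, endpoint and test.** "The primary endpoint for this trial will be the 7 days of treatment with or without GBP and best medical therapy". The next sentence begins "For this endpoint the treatment groups will be compared using a two-tailed test with a p"-value threshold of 0.05.
- **C.6, variables.** "We will compare the NPS, patient satisfaction score and the fentanyl requirement among the GBP and placebo group", by a two-sample t test or a Wilcoxon test. None of the three is marked primary. The same section also says "The calculated total daily NPS score; opioid requirement and GBP dose will be analyzed".
- **Abstract and Specific Aims.** Pain and narcotic requirement are the primary targets, joined by *and* in the hypothesis and listed as two primary aims. Satisfaction is a secondary aim.
- **End of Specific Aims.** The case for adopting gabapentin rests on less pain, better satisfaction, or both. Narcotics are not part of that condition.
- **B. Innovation.** The hypothesis counts as confirmed if narcotic requirements fall; pain is not mentioned in that condition.
- **C.2, goal.** "A decrease in pain score equal or more than 50% will be defined as meeting the goal of the study".
- **C.2, second-line rescue.** "2nd line- enteral /PO oxycodone 5mg PRN q4hrs pain, and if still in pain after next assessment, then 10mg q4hrs PRN". C.4 defines the daily narcotic requirement from fentanyl alone.
- **Daily pain score.** C.2: "Total score over 24 hours will be averaged as daily score". C.4: "We will calculate daily total score for each patient". A.2 and C.6 also use a total; C.5 uses a daily average.
- **C.7.** The null hypothesis concerns pain score and satisfaction. Narcotics do not appear.

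**The concern.** A treatment period is not something two arms can be compared on. The sentence that carries the significance level therefore does not say which measurement, summarised how, decides the trial. This goes beyond missing detail, because the other sections point to different criteria. With 20 patients and several candidate outcomes, the criterion could be settled after the results are known.

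Two things are at stake. If success on either outcome is accepted without adjustment, the stated 5% is not the trial's false-positive rate. If both outcomes are required, the rate is protected, but the power for the trial's conclusion is lower than for each outcome and is stated nowhere. C.1.a hopes the result will support a larger funded trial, so readers need to know which outcome was confirmed.

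The narcotic outcome has a further problem. If the arms move to oxycodone at different rates, a fentanyl-only comparison can misstate the narcotic difference.

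**Working it through.** **1. The plan's own figure.** C.7 gives alpha 0.05, 80% power, SD 5.84, a 25% difference and a sample size below 10. The normal-approximation formula per arm is n = 2 × SD² × (1.960 + 0.842)² / δ². The mean to which 25% applies is not given, so δ must be assumed:

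| Assumed meaning of 25% | δ | n per arm |
|---|---|---|
| of 10 points (full 0–10 range) | 2.5 | 86 |
| of a daily total of 30 | 7.5 | 10 |
| of the maximum daily total, 6 × 10 = 60 | 15 | 3 |

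The figure cannot be confirmed or refuted. The SD's unit is also unclear. The largest SD possible for a 0–10 score is 5, or at most 5 × √(53/52) = 5.05 in a sample of the 53 retrospective patients, and 5.84 exceeds that. C.7 does not state sidedness and gives no narcotic inputs.

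**2. Criteria side by side.**

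| Section | Implied criterion |
|---|---|
| Abstract, Specific Aims (hypothesis) | pain and narcotics |
| End of Specific Aims | pain, satisfaction, or both |
| B. Innovation | narcotics |
| C.2 | pain decrease of at least 50% |
| C.6 | pain score, satisfaction, fentanyl, unranked |
| C.7 null | pain score and satisfaction |

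No section gives an order, an alpha split or a rule for combining outcomes. C.6 does not compare the 50% decrease between arms.

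**3. Either outcome suffices, each at two-sided 0.05.** Familywise error = 1 − P(|Z₁| < 1.96 and |Z₂| < 1.96), with Z₁ and Z₂ bivariate normal. The documents give no correlation, so the values are assumed.

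- Correlation 0: 1 − 0.95² = 9.75%
- Correlation 0.5: 1 − 0.9093 = 9.1%
- Correlation 0.8: 1 − 0.9219 = 7.8%

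Simulated t tests at 10 per arm agree (9.7%, 9.1%, 8.0%). If satisfaction also counted, three independent tests would give 1 − 0.95³ = 14.3%.

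**4. Both required.** A false claim needs a significant result on at least one outcome with no true effect, so its probability cannot exceed 5%. Power falls instead. As an illustration only, two independent outcomes with 80% power each give 0.80 × 0.80 = 64%.

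**5. Narcotic outcome.** C.2 permits oxycodone up to 10 mg every 4 hours, so the ceiling is 10 × 24/4 = 60 mg/day. A fentanyl-only total counts none of it. This is the permitted maximum, not expected use.

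**6. Pain score.** Four-hourly scoring gives six scores a day. With all six present, total = 6 × average and the tests are identical. One missed score removes about 1/6 = 17% of a total without any change in pain; an average is not affected in this way.

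**The case against.** The strongest reply is that the intent is clear. The Specific Aims list two primary aims, C.6 names the compared variables and candidate tests, and C.4 treats the primary endpoint as something completed by day 7. Seven days is then simply the window. This stands as far as it goes. A reader might infer from the endpoint sentence that the trial has no outcome variables at all, and the documents do not support that. What remains open is the summary over the window, which variable carries the significance level, and the success rule.

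It is also fair that *and* in a hypothesis is not a testing rule. Requiring both outcomes is the closest match to the Abstract and the hypothesis, but it is not the only defensible choice.

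A reader might also infer that oxycodone is ignored throughout. C.6 separately mentions opioid requirement, and C.2 has nursing summarise pain scores along with the standard pain plan, so the doses may already be captured. The defect is inconsistency: the between-arm comparison itself names fentanyl. Likewise, total versus average matters only when scores are missed, and no missing rate is given.

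Finally, this is a small trial with pilot aims. Yet the plan itself sets a two-tailed 0.05 test and 80% power, and it draws treatment conclusions from a positive result.

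**Conclusion.** The point holds as a defect of definition: the summary measure and decision rule are missing, and the criteria stated elsewhere conflict. The measurable consequence is a familywise error of about 7.8% to 9.8% against 5%, on two assumptions: that either outcome counts without adjustment, and that the correlation lies between 0 and 0.8. If both are required, there is no inflation.

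A reader might go further and take a joint power such as 64%, or a range up to 84%, as the trial's actual power. The documents do not support that. Those values credit both outcomes with the C.7 power, which cannot be reproduced and has no narcotic inputs. Nor is 64% a floor. If the 80% at 10 per arm was one-sided, two-sided power per outcome is about 69%, and joint power at correlation 0 is 0.686² = 47%.

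The definitional finding depends on none of these power figures. It should be corrected before any between-arm results are seen.

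**What to change.** Replace the C.6 endpoint sentence with two primary outcomes, each one value per patient over study days 1–7:

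1. The mean of the daily average head and neck pain score, with A.2, C.4 and C.6 changed from total to average.
2. Total opioid given for head and neck pain, fentanyl plus oxycodone, with a stated conversion. Align the narcotic definition in C.4 and the comparison in C.6.

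Name one test for each outcome in place of the t-or-Wilcoxon choice.

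State one decision rule in advance that holds 5%: both required (closest to the Abstract and hypothesis), a sole primary outcome, a fixed testing order, or Holm. Because rescue is given as needed in response to the pain score, state under any rule how opposite movements of the two outcomes will be read.

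Keep satisfaction secondary. State whether the 50% decrease is a secondary responder outcome or only the definition of pain control. Align the Specific Aims, B, C.2, C.6 and the C.7 null with the chosen rule.

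Restate the C.7 power for that rule at 10 per arm once the control mean, the SD's unit, the sidedness and the narcotic inputs are given.

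**Cost.** Wording, one conversion, and recording of oxycodone doses if not already done. No patients are added. The stated power will look less favourable if both outcomes are required or under Holm, whose first step tests at 0.025: an outcome with 80% power at 0.05 and 10 per arm has about 70% there. A sole primary or a fixed order avoids that loss for the first outcome.
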